12.1 Study Design/Endpoints

This is an open label, randomized, clinical trial that looks to compare the post-operative bleeding in children who received pathogen-reduced (PR) platelet transfusions versus standard (large volume delayed sampling – LVDS) platelet transfusions.

12.2 Sample Size/Accrual Rate

252 subjects will be randomized 1:1 to pathogen-reduced (PR) platelet transfusions or standard (large volume delayed sampling – LVDS) platelet transfusions. Randomization will be done in REDCap using blocks of varying sizes and stratified by site and STAT score. We anticipate only 50% of children will require a transfusion, leaving evaluable 63 patients per arm. With 63 patients per arm (126 total), and assuming a standard deviation of 0.4, we will have 90% power to detect a minimum mean difference of 0.2 between the two treatment arms with a significance level of 0.050 using a two-sided two-sample equal-variance t-test.

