4.6 Strategies for Recruitment and Retention

All children scheduled to undergo elective cardiopulmonary bypass surgery are seen in the outpatient cardiothoracic (CT) surgery clinic setting approximately 3-5 days prior to surgery. Subjects and their families will be approached for assent/consent at this outpatient visit. Clinical staff at these outpatient sites (at Komansky Children's Hospital at Weill Cornell and Morgan Stanley Children's Hospital at Columbia) will be educated on the inclusion/exclusion criteria and consenting process. They will introduce the study to the families and if willing, the families will be approached by a clinical research coordinator for consent. The number of subjects eligible as well as those enrolled will be logged and reviewed on a monthly basis.

For neonates admitted for their birth and awaiting cardiac surgery, they will be approached in the neonatal intensive care unit by the CT surgery team. The families will be introduced to the study by the CT surgery team and if willing, will be approached by a clinical research coordinator for consent.

Subjects will be enrolled regardless of gender, race, and ethnicity. To demonstrate a difference of 1 mL/kg/hr of post-operative bleeding between the two study groups with 80% power, we will need 126 subjects enrolled and transfused platelets (63 subjects/group). Given the need for randomization prior to the decision to transfuse (as described above in Section 3.1), and the estimate that 50% of patients will not require any platelet transfusions,

we will need to consent and randomize approximately 252 subjects. Given that the two centers perform approximately 500 surgeries per year and the enrollment period will be approximately 18 months, we will require a consent rate of 34%.

We seek to enroll only children, who are considered a vulnerable participant, in order to understand the hemostatic efficacy of PR platelet transfusions in this population. The coagulation systems of infants and children are unique to adults and therefore children must be studied separately. Participants and/or their families will no be compensated for participation in the study.

5. Registration Procedures

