11.2.5 Record Retention

Essential documents are those documents that individually and collectively permit evaluation of the study and quality of the data produced. After completion of the study, all documents and data relating to the study will be kept in an orderly manner by the Investigator in a secure study file. Essential documents should be retained for 2 years after the final marketing approval in an ICH region or for at least 2 years since the discontinuation of clinical development of the IP. In addition, all subjects medical records and other source documentation will be kept for the maximum time permitted by the hospital, institution, or medical practice.

12. Statistical Considerations

Due to feasibility and limited resources, a sample size of 126 patients will be included in this study. A sample size of 63 patients (126 total) in each group achieves 90% power

to detect a minimum difference of 0.2 mL/kg/hr in chest tube output 24 hours after the cardiopulmonary bypass surgery between the group receiving pathogen-reduced (PR) platelet transfusions and the group receiving standard (large volume delayed sampling – LVDS) platelet transfusions using a two-sample t-test assuming equal variance with a two-sided significance level of 0.05.

Based on preliminary data, only around 50% of children who undergo cardiopulmonary bypass surgery require platelet transfusions. Therefore, 252 patients will be enrolled and randomized to the study to take that into consideration.

Descriptive statistics (means, medians, standard deviations, interquartile ranges, proportions, frequency, and percent) will be calculated for baseline characteristics to assess and describe the study participants (by treatment group). Baseline comparability will be assessed using two-sample t-test (or Wilcoxon-rank sum test) for continuous baseline characteristics and the chi-square test (or Fisher's exact test) for categorical baseline characteristics.

Based on the understanding that 50% of the randomized participants will receive treatment, the following populations will be formed for the purpose of data analysis:

- An intent-to-treat cohort, defined as all participants who were recruited into the study, will be used for the primary and secondary analyses in the arm in which they were randomized, regardless of whether treatment was given.
- Per-protocol cohort, defined as all participants that continue with the platelet transfusion (PR platelets or LVDS platelets)

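### The stated 90% power is about 80% on the plan's own inputs, and section 4.6 justifies the same 126 patients with a difference five times larger

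*Combined protocol and SAP*

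**What the plan says.** The power for the primary endpoint, chest tube output over the first 24 hours, is stated in three places.

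- **Section 12.2** starts from 252 randomized children, about half of whom are expected to be transfused: "We anticipate only 50% of children will require a transfusion, leaving evaluable 63 patients per arm". For those 63 per arm it says: "assuming a standard deviation of 0.4, we will have 90% power to detect a minimum mean difference of 0.2 between the two treatment arms". The level and test are given as follows: "with a significance level of 0.050 using a two-sided two-sample equal-variance t-test".
- **Section 12, opening paragraph**, repeats the claim without the SD: "A sample size of 63 patients (126 total) in each group achieves 90% power". The target is worded there as follows: "to detect a minimum difference of 0.2 mL/kg/hr in chest tube output 24 hours after the cardiopulmonary bypass surgery".
- **Section 4.6** gives another basis for the same number: "To demonstrate a difference of 1 mL/kg/hr of post-operative bleeding between the two study groups with 80% power, we will need 126 subjects" (63 per group, transfused). It states no SD. The 252 to be randomized and the required consent rate of 34% are then derived from this figure.

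**The concern.** There are two problems. First, section 12.2 supplies every input to its power calculation, and 63 per arm looks too small for 90% power at a standardized difference of 0.2/0.4 = 0.5. Second, sections 4.6 and 12 reach the same 126 patients from differences that are a factor of five apart, in the same units, and with different power.

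This matters because section 3.1 hypothesizes that the two products give equivalent hemostasis, so a non-significant result is the outcome the investigators expect. Such a result should be read against a known detectable difference and a known chance of missing it. As written, the document offers 0.2 or 1 mL/kg/hr, at 90% or 80% power, and the 90% is not supported by its inputs. An IRB or DSMB relying on sections 12 and 12.2 would take the risk of missing the planned difference to be half of what it is.

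**Working it through.** **Inputs, all from section 12.2:** n = 63 per arm; SD = 0.4; difference = 0.2 (mL/kg/hr, the unit given in section 12); two-sided alpha = 0.05; two-sample equal-variance t-test.

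**Step 1. Attempt to reproduce the 90%.**

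Noncentrality = difference / (SD × √(2/n)) = 0.2 / (0.4 × √(2/63)) = 0.2 / 0.0713 = 2.806, with 2 × 63 − 2 = 124 degrees of freedom.

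- Exact noncentral t: power = 79.5%.
- Normal approximation: Φ(2.806 − 1.960) = Φ(0.846) = 80.1%.

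The 90% is not reproduced. The shortfall is 90 − 79.5 = 10.5 points, and the type II error is 20.5% against 10%.

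**Step 2. Try other readings of the same inputs.**

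| Variant | Power |
|---|---|
| One-sided 0.05, exact t | 87.4% |
| Two-sided 0.10, exact t | 87.4% |
| Wilcoxon test (section 12.4.1 option), efficiency 0.955 under normality | about 78% |
| All 126 randomized per arm, full 0.2 difference in everyone | 97.7% |

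None gives 90%. The last also conflicts with section 12.2, which ties the 90% to 63 evaluable per arm.

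**Step 3. What 63 per arm corresponds to.**

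Normal-approximation sample size: n = 2 × (z₀.₉₇₅ + z_power)² × (SD/difference)².

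- 80% power: 2 × (1.960 + 0.842)² × (0.4/0.2)² = 62.8, so 63 per arm (exact t: 64, power 80.1%).
- 90% power: 2 × (1.960 + 1.282)² × (0.4/0.2)² = 84.1, so 85 per arm (exact t: 86, power 90.3%).

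The plan's 63 is the 80% sample size.

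**Step 4. What would make 90% true with 63 per arm (exact t).** Either a difference of 0.233 at SD 0.4, or an SD of 0.344 at a difference of 0.2. At 80% power the detectable difference is 0.201.

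**Step 5. Section 4.6 against section 12.2.**

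- At SD 0.4, a difference of 1 mL/kg/hr needs 4 per arm for 80% power (exact t; the normal approximation gives 3). With 63 per arm, power is essentially 100%.
- For 63 per arm to give 80% power at a difference of 1, the SD must be about 1.99 mL/kg/hr, and 1.99/0.4 is about 5.

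Sections 4.6 and 12.2 therefore imply SDs about five times apart for the same endpoint.

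**The case against.** The strongest reply does not defend the 90%; it disputes the consequences and the remedy.

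- **Pilot sized by feasibility.** Section 12 says that feasibility and limited resources set the size. That can justify 126 patients, but it does not make the power statement correct.
- **The target is not really in doubt.** The statistical section gives 0.2 twice, and the outlier is one sentence in the recruitment section. This has some force, but that sentence is an explicit power statement from which the 252 and the consent rate are derived, so it needs correcting.
- **A null result will be read from the confidence interval** promised in section 12.4.1. That is true of the estimate. It does not repair the planned type II error or say which difference the trial was designed to detect.
- **Rounding.** A difference of 0.233 prints as 0.2, and modest rounding of both inputs would also do: 0.21/0.36 = 0.583, against the 0.233/0.4 = 0.582 needed for 90%. The 90% may have come from unrounded inputs. If so, the printed inputs are wrong instead of the power, and the statement still needs correction.
- **Which figure is wrong is an inference.** The 80% in section 4.6 matches the power recomputed for 0.2, which suggests that the 90% and the 1 mL/kg/hr are the two errors. The documents give no source for the SD of 0.4, so the sponsor must confirm. This stands.
- **The 80% applies to the transfused children only.** Section 12 assigns the primary analysis to everyone randomized. If the product had no effect in the untransfused half and the SD stayed at 0.4 (both assumptions), the difference would be 0.1 with 126 per arm and power about 51%. This is a separate issue, but the corrected sentence should name its population.

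**Conclusion.** The concern holds in both parts. On the inputs printed in section 12.2, power is 79.5% (80.1% by normal approximation), not 90%, and the type II error is about double what the plan states. This needs no figure from outside the document; it assumes only the stated t-test, a common SD of 0.4 and 63 evaluable transfused patients per arm. Separately, section 4.6 states a target five times larger, with different power, for the same 126 patients, and it agrees with section 12.2 only if the SD is about 2.0 instead of 0.4. That the statements conflict is certain. Which input is mistaken is for the sponsor to confirm. The point must be fixed because it is a wrong figure for the primary endpoint, stated twice and contradicted elsewhere in the protocol.

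**What to change.** 1. **Sections 12 and 12.2:** replace the 90% claim with a statement that 63 transfused patients per arm give about 80% power for a difference of 0.2 mL/kg/hr at SD 0.4 (equivalently, 90% power for 0.233 mL/kg/hr), two-sided 5%, equal-variance t-test.
2. **Section 4.6:** replace the 1 mL/kg/hr target with the same difference, SD and power, so that the document carries one power statement.
3. **Before editing,** the sponsor should confirm the intended difference and SD from the source calculation, and section 12.2 should say where the SD of 0.4 comes from.

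The cost is wording in three places and a less favourable stated power. Enrolment, conduct and analysis do not change. If the sponsor preferred to keep 90% for 0.2 mL/kg/hr, the plan would need 86 evaluable per arm, or 2 × 86 / 0.5 = 344 randomized instead of 252. That is not requested here.

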12.3 Stratification Factors

Subjects will be stratified by site and STAT score (1/2 vs. 3/4/5).

12.4 Analysis of Endpoints

12.4.1 Analysis of Primary Endpoints

The primary endpoint in this study is the chest tube output for the first 24 hours following cardiopulmonary bypass surgery. A two-sample t-test assuming equal variance or a non-parametric Wilcoxon rank-sum test will be used, as appropriate. All tests will be two-sided with an alpha level of 5%. Confidence intervals for the difference in means will also be calculated to assess precision.

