3.1 Overall Design

This is a multisite, open-label, randomized trial of PR versus LVDS platelet transfusions in children undergoing cardiopulmonary bypass surgery. The study will be conducted at Komansky Children's Hospital at Weill Cornell and Morgan Stanley Children's Hospital at Columbia. Given that both products are FDA approved and already used in this patient population, it is a Phase IV study. Based on our preliminary retrospective data, we hypothesize that both products will have equivalent hemostasis, as measured by chest tube output in the first 24 hours, as well as total blood component requirements. Given the complexity of surgery is associated with bleeding risk, the two groups will be stratified on a validated score of surgical complexity (STS scoring). All subjects will be enrolled in the study for the length of their hospitalization.

The need for platelet transfusion will not be dictated by the study intervention, but rather the clinical team (both in the operating room and post-operatively, in the pediatric intensive care unit). Given that we do not want to delay the release of blood products from the blood bank, but rather have them available as standard of care in the operating

room, we cannot randomize the subjects at the time of the decision to transfuse platelets. Therefore, we will randomize subjects before the day of surgery. We recognize that there will be a significant number of randomized subjects (approximately 50%) who do not receive a platelet transfusion. Data will be collected on this group and analyzed both separately, and in an intention to treat model.

All platelet transfusions will be given as 10mL/kg as is considered standard of care.

Given the need to cross-check any transfusion of the blood component for patient safety, no area of the labeling will be disturbed and therefore the clinicians caring for the patients will be unblinded. Those responsible for data entry and data analysis will be blinded to the assigned groups of the subjects.

To minimize bias, we will perform subgroup analyses of neonates versus all other children given that the neonatal coagulation system is still under development and different than the coagulation system of the older child.

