7.11 Measures to Minimize Bias: Randomization and Blinding

Stratified and permuted blocked randomization will be performed. A series of randomized blocks with a defined block size will be generated for each participating site with a 1:1 allocation ratio. This will allow for an equal number of patients in the PR platelets group and LVDS platelets group at each participating site (even in the event that full target accrual is not achieved). Randomization will be stratified by site (Komansky Children's Hospital/Weill Cornell vs. Morgan Stanley Children's Hospital/Columbia) and STAT score (STAT 1/2 vs. STAT 3/4/5). A biostatistician from the Weill Cornell CTSC Biostatistics, Epidemiology and Research Design (BERD) Core will create the randomization list and will not be involved with the study. The randomization list for each site will also reside in the Research Pharmacy at each site. Only the BERD statistician and the Research Pharmacies will have a copy of the blocked randomization list (for their respective sites). As this is an open-label study, all study personnel will be aware of the treatment assignments. The blocked randomization schemes for each participating site will be uploaded to a central REDCap database (housed at Weill Cornell Medicine) and each site's Research Pharmacy will be able to randomize a patient at their site by using the REDCap randomization module.

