12.4.2 Analysis of Secondary Endpoints

There are three secondary endpoints in this study. First, we will compare the total dose red blood cell transfusions in the first 48 hours between the two arms. Secondly, we will compare the total blood products transfused (intra and post-operatively) in the first 48 hours between the two arms. Lastly, rate of nosocomial infections between the two treatment arms will be compared. For the first two secondary endpoints, the two-sample t-test or non-parametric Wilcoxon rank-sum test will be used, as appropriate. For the last secondary endpoint, a Chi-square test or Fisher's exact test will be used as appropriate.

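### The primary and the two continuous secondary tests ignore the site and STAT strata used in randomisation; they stay valid but give away precision

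*Combined protocol and SAP*

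**What the plan says.** Section 7.11 states: "Stratified and permuted blocked randomization will be performed". Section 12.2 names the factors: "Randomization will be done in REDCap using blocks of varying sizes and stratified by site and STAT score". Section 12.3 repeats them and groups STAT as 1/2 versus 3/4/5, so there are 2 × 2 = 4 strata. Section 3.1 explains the choice: "Given the complexity of surgery is associated with bleeding risk, the two groups will be stratified on a validated score of surgical complexity".

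The analysis sections do not return to these factors. For chest tube output, section 12.4.1 says: "A two-sample t-test assuming equal variance or a non-parametric Wilcoxon rank-sum test will be used, as appropriate". It adds: "Confidence intervals for the difference in means will also be calculated to assess precision". Section 12.4.2 says: "For the first two secondary endpoints, the two-sample t-test or non-parametric Wilcoxon rank-sum test will be used, as appropriate". The opening of section 12 sets the population: "An intent-to-treat cohort, defined as all participants who were recruited into the study, will be used for the primary and secondary analyses".

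No stratified test, covariate-adjusted model or sensitivity analysis using the strata appears anywhere. The neonate subgroup analysis in section 3.1 uses a different factor.

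**The concern.** Allocating within strata forces the arms to have nearly the same mix of sites and surgical complexity. Differences between strata therefore hardly contribute to the observed difference between arms. A plain t-test does not know this: its pooled variance still contains the between-stratum variation. The reported standard error is then larger than the true one, the confidence interval is too wide, and the test rejects less often than its nominal 5%. The rank-sum test is conservative for the same reason.

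Precision matters here for three reasons. Section 3.1 expects the products to be equivalent, so the confidence interval will carry much of the conclusion. The intent-to-treat cohort is expected to be about half untransfused, which can dilute any effect. The opening of section 12 says the sample size is limited by feasibility and resources.

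**Working it through.** **Inputs from the documents.** SD 0.4, difference 0.2 mL/kg/hr, 252 randomised 1:1, half transfused, 63 evaluable per arm (section 12.2); two-sided alpha 5% (section 12.4.1); four strata (section 12.3).

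**Assumptions.** R² is not given, so 0, 5, 10, 20 and 30% are used. The base case takes an even split by site and STAT, lets STAT carry all the stratum variance, and uses blocks of 4 or 6. Total SD is held at 0.4.

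**1. The plan's own power.** Standard error = 0.4 × √(2/63) = 0.0713, and 0.2/0.0713 = 2.81. Power is Φ(2.81 − 1.96) = 80.1%, or 79.5% by the noncentral t. The stated 90% does not reproduce; it needs 85 per arm. The unadjusted baseline among transfused children is therefore about 80%.

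**2. What R² means in bleeding.** With an even STAT split, the between-stratum variance is gap²/4. So gap = 2 × 0.4 × √R² = 0.8√R², which gives the second column below.

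**3. Standard error and size.** With balanced strata the true standard error is √(1−R²) times the one the t-test reports, so

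- SE ratio (unadjusted/adjusted) = 1/√(1−R²)
- unadjusted type I error ≈ 2 × [1 − Φ(1.96/√(1−R²))] = 5.0, 4.4, 3.9, 2.8 and 1.9%

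For 126 per arm the unadjusted 95% half-width is 1.96 × 0.4 × √(2/126) = 0.099 mL/kg/hr. At R² = 20% the adjusted one is 0.099 × 0.894 = 0.088.

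**4. Intent-to-treat cohort, simulated** (6,000 trials per setting; Monte Carlo error about √(0.05 × 0.95/6000) = 0.3 points for size and √(0.5 × 0.5/6000) = 0.6 for power). Power is for a 0.2 effect in the transfused half only, an average of 0.1.

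| R² | STAT gap (mL/kg/hr) | SE ratio | Type I unadj. | Type I adj. | Power unadj. | Power adj. |
|---|---|---|---|---|---|---|
| 0% | 0 | 1.00 | 5.1% | 5.1% | 50.2% | 50.1% |
| 5% | 0.18 | 1.03 | 4.1% | 4.5% | 49.6% | 51.7% |
| 10% | 0.25 | 1.05 | 3.9% | 4.8% | 48.7% | 52.8% |
| 20% | 0.36 | 1.12 | 2.8% | 5.0% | 49.5% | 58.4% |
| 30% | 0.44 | 1.20 | 1.9% | 4.8% | 51.2% | 65.0% |

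If the effect is 0.2 in all children, power is already 97.8 to 99.1% unadjusted and 97.8 to 99.8% adjusted, a gain under 1 point.

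**5. Transfused children (about 126), simulated power, same order of R².**

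- Transfusion independent of STAT: unadjusted 79.2, 79.3, 78.9, 80.1, 80.9%; adjusted 78.8, 80.4, 82.1, 87.4, 91.1%.
- Transfusion in 20% of STAT 1/2 and 80% of STAT 3/4/5: unadjusted 79.9, 81.0, 80.4, 82.7, 84.5%; adjusted 79.4, 81.4, 82.5, 86.9, 90.5%.

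**6. Rank tests, intent-to-treat, shift 0.1** (4,000 trials). Type I error: Wilcoxon 4.6, 4.1, 4.4, 3.1, 1.7%; van Elteren 4.6, 4.7, 5.0, 5.0, 4.9%. Power: Wilcoxon 49.9, 49.3, 49.2, 47.3, 46.0%; van Elteren 49.4, 50.2, 53.1, 56.9, 63.0%.

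**7. Cross-check under other assumptions.** With 40% of children in STAT 3/4/5, a fifth of the stratum variance due to site, blocks of 2, 4 or 6 and R² = 20%, all 252 analysed: type I error 3.0% unadjusted and 5.6% adjusted (4,000 trials, error about 0.35 points); power for a 0.1 difference 49.6% and 60.4% (800 trials).

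**The case against.** The strongest reply is that the loss is conditional and may be small. The documents say only that complexity is associated with bleeding; they do not say how strongly, and nothing says that site matters. An R² of 10% already needs a STAT gap of 0.25 mL/kg/hr, more than the treatment difference the trial is sized for. Up to that point the gain is about 3 points among transfused children and about 4 in the diluted intent-to-treat case. This stands, and is why the whole range is shown; the top of it is demanding.

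The planned t-test is also the one used for the sample size, and section 7.11 gives equal numbers per arm at each site as a purpose of the blocking. That makes the plan coherent, but section 3.1 gives bleeding risk as the reason for stratifying on complexity, and only the analysis can use that.

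The fall to about 50% power comes from dilution, not from ignoring strata, and section 12.2 gives the SD of 0.4 for evaluable children, not for the mixed cohort. Both points are right. Only the differences between the unadjusted and adjusted columns belong to this concern.

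Finally, a linear model can lose to Wilcoxon under skew. With an assumed lognormal outcome (mean 0.6, SD 0.4) in the transfused half, Wilcoxon against the linear model gave 71.6 vs 66.6% at R² = 0, 71.9 vs 70.6% at 10% and 71.4 vs 73.4% at 20%. This bears on the choice between mean and rank methods. Like for like (linear model for t-test, van Elteren for Wilcoxon), adjustment still gains under skew once R² reaches 10%. In the intent-to-treat cohort the linear model is within about 1.5 points of Wilcoxon or better.

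**Conclusion.** The concern holds, as a loss of efficiency and not a bias. If the strata predict bleeding, the planned tests have size below 5%, intervals wider than necessary and lower power than the same data allow. The size depends on R², which the documents do not give. At 10% the standard error is 5% too large, and adjustment adds about 4 power points in the diluted intent-to-treat case and 2 to 3 among transfused children. At 20% the figures are 12%, about 9 points, and 4 to 7 points. At R² = 0 there is nothing to gain, and if the effect reaches all children the gain is under 1 point.

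The statement that the test stays valid covers only the omission of strata in the randomised comparison. It does not cover the transfused set, which is selected after randomisation in an open-label trial, the open choice between t-test and Wilcoxon, or the interim looks in section 12.5. The infection comparison in section 12.4.2 also ignores the strata; its loss was not quantified here. The change should be made, because it costs almost nothing and real power is nearer 80% than the stated 90%.

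**What to change.** In section 12.4.1, pre-specify as primary a linear model of chest tube output (mL/kg/hr) on arm, site and STAT stratum (1/2 vs 3/4/5) in the intent-to-treat cohort. Report the adjusted difference with its 95% confidence interval. Use the same model in the per-protocol cohort. If a rank test is used, make it the van Elteren test over site × STAT, and settle its role in advance. Keep the unadjusted test as a sensitivity analysis. Make the same change in section 12.4.2 for red cell dose and total blood products.

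Use the strata as recorded at randomisation. Sections 3.1 and 6.1.1 call the complexity score STS and do not list site as a factor, so their wording should be aligned with sections 7.11, 12.2 and 12.3.

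The cost is SAP wording and a few lines of R. Both factors are known at randomisation, so no data are added, and the model spends two degrees of freedom. If the strata explain nothing, simulated power falls by about 0.5 point or less (79.2% to 78.8% in the transfused half), and by about 1 point for van Elteren there (75.9% to 74.5%).
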